Attachment 2. Biochemical Analytical Plan in Children and Adults.

Laboratory and Contact	Analyte	* CLIA Cert.	Matrix	Volume	Reportable Range, Guidelines, Critical Values Reference ranges will be updated when commercial lab is selected.
Children and Adults					
Commercial Laboratory (to be determined)* Contact:	Lipids Total cholesterol, fasting Triglycerides, fasting Low Density Lipoprotein (LDL), fasting	Yes	Serum	0.5 ml (for all)	Coronary Heart Disease Risk (CHD)1Adult, 18+ years:Desirable: <200 mg/dL

¹https://www.mayomedicallaboratories.com/test-catalog/Clinical+and+Interpretive/8320

		Adult, 18+ years:
		Desirable: <100 mg/dL
		Above Desirable: 100-129 mg/dL
		Borderline high: 130-159 mg/dL
		High: 160-189 mg/dL
		Very high: ≥190 mg/dL
		Child, 2-17 years:
		Acceptable: <110 mg/dL
		Borderline high: 110-129 mg/dL
		High: ≥130 mg/dL
		CHD Risk ¹
		Adult, 18+ years:
		Males: ≥40 mg/dL
		Females: ≥50 mg/dL
High Density Lipoprotein (HDL), fasting		
		Child, 2-17 years:
		Low: <40 mg/dL
		Borderline low: 40-45 mg/dL
		Acceptable: > 45 mg/dL

Attachment 2. Biochemical Analytical Plan in Children and Adults.

Laboratory and Contact	Analyte	* CLIA Cert.	Matrix	Volume	Reportable Range, Guidelines, Critical Values Reference ranges will be updated when commercial lab is selected.
Children and Adults					
	Uric Acid				Males ² ≤ 8.0 mg/dL Females ≤ 6.1 mg/dL Males ³
Commercial Laboratory (to be determined)* Contact:	Creatinine (to estimate glomerular filtration rate [eGFR])	Yes	Serum	1 ml	1-2 years: 0.1-0.4 mg/dL 3-4 years: 0.1-0.5 mg/dL 5-9 years: 0.2-0.6 mg/dL 10-11 years: 0.3-0.7 mg/dL 12-13 years: 0.4-0.8 mg/dL 14-15 years: 0.5-0.9 mg/dL > or =16 years: 0.8-1.3 mg/dL Reference values have not been established for patients that are <12 months of age. Females 1-3 years: 0.1-0.4 mg/dL 4-5 years: 0.2-0.5 mg/dL 6-8 years: 0.3-0.6 mg/dL 9-15 years: 0.4-0.7 mg/dL > or =16 years: 0.6-1.1 mg/dL Reference values have not been established for patients that are <12 months of age. ESTIMATED GFR >60 mL/min/BSA Note: eGFR results will not be calculated for patients <18 or >70 years old.

² https://www.mayomedicallaboratories.com/test-catalog/Clinical+and+Interpretive/8440
 ³ https://www.mayomedicallaboratories.com/test-catalog/Clinical+and+Interpretive/8472

Laboratory and Contact	Analyte	* CLIA Cert.	Matrix	Volume	Reportable Range, Guidelines, Critical Values Reference ranges will be updated when commercial lab is selected.
Children and Adults					
Commercial	Thyroid Hormones				
Commercial	Thyroid Stimulating Hormone (TSH)				0.30-3.0 mIU/L ⁴
Laboratory (to be determined)*	Free Total Thyroxine (Free T4)	Yes	Serum	0.5 ml	0.8-2.0 ng/dL
Contact:	Total Thyroxine (TT4)				4.5-12.5 μg/dL
	Total Triiodothyronine (TT3)				80-180 ng/dL
	Liver Tests	-			
	Alanine transaminase (ALT)	-			15-65 U/L ⁵
	Aspartate transaminase (AST)	-			5-40 U/L
	Alkaline phosphatase (ALP)				Female: 50-136 U/L;
		-			
	Gamma-glutamyltransferase (GGT)				Male 5-85 U/L
Commercial Laboratory (to be determined)*	Albumin (Alb)	Yes	Serum	0.5 ml standard tests;	3.4-5.0 g/dL Critical Value: <1.5 g/dL Critical Value: >7.9 g/dL
Contact:	Total bilirubin (TBIL)			СК18	0.0 – 1.0 mg/dL Critical Value: >12.9 mg/dL
	Direct bilirubin (Conjugated Bilirubin)				0.0-0.3 mg/dL
	Non-alcoholic fatty liver disease (NAFLD)/steatohepatitis				
	Cytokeratin 18 M30 (CK-18 M30) Cytokeratin 18 M65 (CK-18 M65)				No evident liver disease: M30 <200 U/L and M65 <300 U/L TASH: M30<200 U/L and M65 >300 U/L Other liver disease: M30: >200 U/L

⁴ University of Southern California Clinical Laboratories Endocrine Services.

⁵ University of Louisville Department of Medicine, Gastroenterology (updated 14 October 2015).

Attachment 2. Biochemical Analytical Plan in Children and Adults.

Laboratory and Contact	Analyte	* CLIA Cert.	Matrix	Volume	Reportable Range, Guidelines, Critical Values Reference ranges will be updated when commercial lab is selected.		
Children and Adults							
Commercial Laboratory (to be determined)* Contact:	Sex Hormones Testosterone Estradiol	Yes	Serum	0.5 ml	Males ⁶ 4-9 years: <7-20 ng/dL	dL dL L ng/dL ng/dL lL L L L Reference Range <lod-13 ml
<lod-16 ml
<lod-26 ml
<lod-38 ml
10-40 pg/mL</lod-38></lod-26></lod-16></lod-13>	

 ⁶ https://www.mayomedicallaboratories.com/test-catalog/Clinical+and+Interpretive/83686
 ⁷ https://www.mayomedicallaboratories.com/test-catalog/Clinical+and+Interpretive/81816

		Females	
		Tanner Stages	Mean Age
		Stage I (>14 days prepubertal)	and 7.1 years
		Stage II	10.5 years
		Stage III	11.6 years
		Stage IV	12.3 years
		Stage V	14.5 years
		ADULTS Males: 10-40 pg/n Females Premenopausal: 1 Postmenopausal: **E2 levels vary w menstrual cycle.	nL .5-350 pg/mL** <10 pg/mL v idely through the
		CHILDREN ⁸ Males	
		Tanner Stages	Reference Range
		Stage III1Stage IV1Stage V1Stage V1ADULTSMales: 10-40 pg/mLFemalesPremenopausal: 15-350 pgPostmenopausal: <10 pg/r	31-167 nmol/L
		Stage II	49-179 nmol/L
		Stage III	5.8-182 nmol/L
Say barmana hinding glabulin (SHPC)		Stage IV	14-98 nmol/L
Sex normone-binding globulin (SHBG)		Stage V	10-57 nmol/L
		Females	
		Tanner Stages	Reference Range
		Stage I	43-197 nmol/L
		Stage II	7.7-119 nmol/L
		Stage III	31-191 nmol/L

⁸ https://www.mayomedicallaboratories.com/test-catalog/Clinical+and+Interpretive/9285

				Stage IV	31-166 nmol/L
				Stage V	18-144 nmol/L
				U U	
				ADULTS	
				Males: 10-57 nm	iol/L
				Females (non-pro	egnant): 18-144 nmol/L
				Males ⁹	
				4-6 years: < or =6	5.7 IU/L
				7-8 years: < or =4	4.1 IU/L
				9-10 years: < or =	=4.5 IU/L
				11 years: 0.4-8.9	IU/L
				12 years: 0.5-10.	5 IU/L
				13 years: 0.7-10.	8 IU/L
				14 years: 0.5-10.	5 IU/L
				15 years: 0.4-18.	5 IU/L
				16 years: < or =9	.7 IU/L
				17 years: 2.2-12.	3 IU/L
				≥18 years: 1.0-18	3.0 10/L
				Females	
Follicle stimulating normone (FSH)				15 days-6 years:	< or =3.3 IU/L
				7-8 years: < or =1	11.1 IU/L
				9-10 years: 0.4-6	.9 IU/L
				11 years: 0.4-9.0	
				12 years: 1.0-17.	
				13 years. 1.0-9.9	10/2
				17 years: 1 2-9 6	
				>18 years:	10/2
				Premenopausal	
				Follicular: 3.9-8.8	3 IU/L
				Midcycle: 4.5-22	.5 IU/L
				Luteal: 1.8-5.1 IU	J/L
				Postmenopausal	: 16.7-113.6 IU/L
Insulin-like growth factor (IGF-1)					
	Follicle stimulating hormone (FSH) Stage IV Stage V ADULTS Males: 10-57 nm Remales (non-pr Males? 4-6 years: < or =				

⁹ https://www.mayomedicallaboratories.com/test-catalog/Clinical+and+Interpretive/8670

Laboratory and Contact	tory and Analyte		Matrix	Volume	Reportable Range, Guidelines, Critical Values Reference ranges will be updated when commercial lab is selected.
Children and Adults		-		2	
Commercial	Immune Function				
Laboratory (to be determined)* Contact:	lg A, lg G, lg M, lg E		Serum	1 ml	
	Glycemic Parameters				
Commercial	Glycosylated hemoglobin (HbA1c)		Whole Blood EDTA	1 ml; plus 1 ml reserve	Diabetes Risk¹⁰ Normal: <5.7% Increased Risk Diabetes: 5.7-6.4% Diabetes: ≥6.5% (confirmation required)
Laboratory (to be	Glucose, fasting, 8-hour Insulin			0.5 ml	
determined)*				Glucose/	<17 μU/ml ⁸
contact:	Glutamate Decarboxylase -65 (Anti-GAD 65)		Serum	Insulin; 1 ml	Negative Antibody: DK≤33 ⁸ Positive Antibody: DK>33
	Thurseine Dheenhetere like Drotein Autoentihedies (Anti 142)			antibodie	Negative Antibody: DK<5 ⁸
	myrosine prosphatase-like protein Autoantibodies (Anti-IAZ)			S	Positive Antibody: DK≥5
Children Only					
Commercial Laboratory (to be determined)* Contact:	Antibodies to measles, mumps, rubella, tetanus, and diphtheria	Yes	Serum	1 ml	
		Serum - 9n Red Top 2	nl Whole Blood – 2 ml Urine – 16 ml x10 ml EDTA Lavender Top 3 ml		

Adults Only				
	Autoimmune Parameters	Yes	Serum	

¹⁰ American Diabetes Association. Standards of Medical Care in Diabetes - 2011. Diabetes Care. January 2011;34(Supplement 1):S11-S61 (subject to periodic update).

	Rheumatoid Factor (RF)				< 15 IU/mL ¹¹
Commercial Laboratory (to be determined)* Contact:	Antinuclear Antibody (ANA) screen			2 ml (for all)	< or =1.0 U (negative) ¹² 1.1-2.9 U (weakly positive) 3.0-5.9 U (positive) > or =6.0 U (strongly positive)
	Antinuclear Antibody (ANA) titer				
		ļ	Adult Total	Serum – 1 Red Top 3	L ml Whole Blood – 2 ml Urine – 16 ml x 10 ml EDTA Lavender Top 3 ml

 ¹¹ https://www.mayomedicallaboratories.com/test-catalog/Clinical+and+Interpretive/9060
 ¹² https://www.mayomedicallaboratories.com/test-catalog/Clinical+and+Interpretive/9026

Attachment 3 – Justification for Sample Size Calculations (Supporting information)

- Attachment 3a Child Sample Size Calculations
- Attachment 3b Adult Sample Size Calculations

Sample size calculations were conducted using OpenEpi Version 3.03 (Dean AG, Sullivan KM, Soe MM. OpenEpi: Open Source Epidemiologic Statistics for Public Health, www.OpenEpi.com, updated 2014/09/22). For some health-related endpoints, calculations could not be conducted because of a lack of information in the studies on the parameters needed to make the calculations.

Sample size calculation for mean difference:

$$n_{1} = \frac{(\sigma_{1}^{2} + \sigma_{2}^{2} / \kappa)(z_{1-\alpha/2} + z_{1-\beta})^{2}}{\Delta^{2}}$$
$$n_{2} = \frac{(\kappa * \sigma_{1}^{2} + \sigma_{2}^{2})(z_{1-\alpha/2} + z_{1-\beta})^{2}}{\Delta^{2}}$$

The notation for the formulae are:

$$n_1 = \text{sample size of Group 1}$$

 $n_2 = \text{sample size of Group 2}$
 $\sigma_1 = \text{standard deviation of Group 1}$
 $\sigma_2 = \text{standard deviation of Group 2}$
 $\Delta = \text{ difference in group means}$
 $\kappa = \text{ratio} = n_2/n_1$
 $Z_{1-\alpha/2} = \text{two-sided Z value (eg. Z=1.96 for 95\% confidence interval).}$
 $Z_{1-\beta} = \text{power}$

Where N_2/N_1 is the ratio of the two sample sizes. Then N_2 is simply this ratio multiplied by N_1 . For a type 1 error (or α error) of .05, the $Z_{1-\alpha/2}$ value is 1.96. This calculation is for a two-tailed hypothesis test and equivalent to using a 95% confidence interval to determine statistical significance. For a one-tail test with α =.05, the $Z_{1-\alpha/2}$ in the above equation is replaced by $Z_{1-\alpha}$ and its value is 1.65, equivalent to using a 90% confidence interval to determine statistical significance. For 80% confidence interval to determine statistical significance. The $Z_{1-\beta}$ in the above equation is the Z value for the selected power. For 80% power, $Z_{1-\beta} = 0.84$, for 90% power, $Z_{1-\beta} = 1.28$, and for 95% power, $Z_{1-\beta} = 1.65$. (See Rosner B. Fundamentals of Biostatistics, 7th Edition, equation 8.27, p. 302).

Fleiss JL. Statistical Methods for Rates and Proportions. John Wiley & Sons, 1981.

Note: In some studies, the standard deviation is not presented but instead, the interquartile range (IQR) is given. Assuming a normal distribution for the outcome under evaluation (e.g., thyroid function measures), the standard deviation can be calculated by dividing the IQR range by 1.35. However if the outcome is not normally distributed, this formula could underestimate the standard deviation. In particular, if the outcome under evaluation has been log-transformed presumably to achieve a normal distribution, the untransformed outcome is unlikely to have a normal distribution. Therefore, using this formula when the outcome does not have a normal distribution may underestimate the SD by as much as 20% according to simulations conducted in Wan X. 2014. A higher SD would increase the sample size requirement.

Attachment 3a. Sample Size for Child Study

The following notes provide comments and information on the parameters (e.g., standard deviation, disease prevalence) used in the sample size calculations provided in Table 1 for the children study.

Sample size calculations were conducted with type 1 (" α error") set at .05 and type 2 error (" β error) set at .20. Sample sizes per stratum group were calculated. It was considered important that a study have a total sample size so that exposures could be categorized into tertiles (i.e., reference level, medium level, and high level) or quartiles (i.e., reference level, low, medium and high).

Studies were selected that were considered the most representative of U.S. populations exposed via drinking water to PFOA, PFOS and/or PFHxS as a result of the migration of these PFAS chemicals into ground water or surface water sources from the use of aqueous film forming foam (AFFF). The PFOS, PFOA and PFHxS results in the NHANES studies were used in many of the sample size calculations. For those outcomes not included in NHANES studies, the C8 studies were used. Where applicable studies from Taiwan or other major industrialized countries were also used.

Examples:

Lipids

In the C8 study (Frisbee 2010), the mean total cholesterol level in the study population was 160.7 mg/dL and the standard deviation (SD) was 29.3. The sample size calculations assumed the same SD in children exposed and the unexposed group. For hypercholesterolemia (total cholesterol \geq 170 mg/dL), the prevalence in the C8 study was 34.2%.

Uric Acid

In the NHANES study (Geiger 2013), the mean uric acid level in the study population was 5.07 mg/dL with a SD of 1.19. The sample size calculations assumed the same SD in the exposed children and the unexposed group. The prevalence of hyperuricemia (uric acid \geq 6 mg/dL) in the NHANES study was 16%.

Kidney Function

The mean estimated glomerular filtration rate (eGFR) in the C8 study of children and adolescents (Watkins 2013) was 133 mL/min/1.73 m² with a SD of 23.9. The sample size calculations assumed the same SD in the exposes children and the unexposed group.

Attention Deficit/Hyperactivity Disorder (ADHD)

In the C8 study (Stein 2011), the prevalence of participant-reported ADHD was 12.4% and the prevalence for participant-reported + used medications for ADHD was 5.1%. Sample size calculations used the 12.4% prevalence.

Hypersensitivity-related Outcomes

From an NHANES study (Stein 2016), the prevalence of current asthma and rhinitis among those aged 12-19 were 10.9% and 25.6%, respectively. For atopic dermatitis, the prevalence for children and adolescents (ages 5-17) is about 12% based on data from the National Health Interview Survey.

Sex hormones and Insulin-like growth factor – 1 (IGF-1)

C8 study of children (Lopez-Espinosa 2016)

a. Testosterone

For PFOS, there was a -6.6% difference in the natural log testosterone among girls (per interquartile range of the natural log of PFOS). Among girls, the median testosterone level was 15 ng/dL with an IQR of <LOD, 21 and the LOD of 10 ng/dL. For the sample size calculation of mean difference, the standard deviation was assumed to be equal for the exposed and unexposed groups and equal to 11.85. (Assuming LOD/2 was the lower limit of the IQR, the range = 21 - 5 = 16. Assuming a normal distribution, dividing 16 by 1.35 converts the IQR to a standard deviation, which equaled 11.85)¹. To obtain the mean difference, the median testosterone level (15 ng/dL) was assumed to be the reference level (i.e., the level among the unexposed). The natural log of the median equals 2.71. A 6.6% decrease equals 2.53. Exponentiating 2.53 equals 12.55. The mean difference is then 15 - 12.55 = 2.45.

Assuming a 95% CI and 80% power, the sample size = 368/group; for a ratio of 2, the sample sizes = 552 and 276.

b. IGF-1

For PFHxS, there was a -2.5% difference in the natural log IGF-1 among boys (per interquartile range of the natural log of PFHxS). Among boys, the median IGF-1 level was 147 ng/mL with an IQR of 116, 187. For the sample size calculation of mean difference, the standard deviation was assumed to be equal for the exposed and unexposed groups and equal to 52.6. (The IQR range was 187 - 116 = 71. Assuming a normal distribution, dividing 71 by 1.35 converts the IQR to a standard deviation, which equaled 52.6)¹. To obtain the mean difference, the median IGF-1 level (147 ng/mL) was assumed to be the reference level (i.e., the level among the unexposed). The natural log of the median equals 4.99. A 2.5% decrease equals 4.865. Exponentiating 4.865 equals 129.7. The mean difference is then 147 - 129.7 = 17.3.

Assuming a 95% CI and 80% power, the sample size = 146/group; for a ratio of 2, the sample sizes = 218 and 109.

For PFOS, there was a -5.9% difference in the natural log IGF-1 among boys (per interquartile range of the natural log of PFOS). This would require considerably smaller sample sizes for IGF-1 than those for PFHxS.

Thyroid function – Children/Adolescents

Taiwan study of children. (Lin 2013)

a. For males aged 12-19, there was a mean difference in the log TSH of -.50 mIU/L for PFOA levels in the 90th percentile (>9.71 ng/ml) compared to the reference level of PFOA exposure. The standard error for the reference group was 0.26 with N=32 in this group; and the standard error for the 90th percentile group was 0.33

with N=6. The standard deviations for the reference and 90th percentile groups were therefore 1.47 and 0.81, respectively.

Assuming a 95% CI and 80% power, the sample size = 89/group; for a ratio of 2, the sample sizes = 158 and 79.

b. For females aged 12-19, there was a mean difference in the log TSH of -.35 mIU/L for PFOA levels in the 90th percentile (>9.71 ng/ml) compared to the reference level of PFOA exposure. The standard error for the reference group was 0.18 with N=71 and the standard error for the 90th percentile group was 0.24 with N=14. The standard deviations for the reference and 90th percentile groups were therefore 1.52 and 0.90, respectively.

Assuming a 95% CI and 80% power, the sample size = 200/group; for a ratio of 2, the sample sizes = 348 and 174.

Additional notes:

Sample sizes for the categorical outcomes in Table 1 were based on the following prevalence in children (also listed in Appendix C Table 1):

Hypercholesterolemia: 34.2% Hyperuricemia: 16% Thyroid disease: 0.6% ADHD 12.4% reported only; 5.1% reported with additional reporting on medications used for ADHD Asthma: 11% Rhinitis: 25.6% Atopic dermatitis: 10.7% Hypertension: 23.4% Obesity: 17%

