4 The proposed sample size of 2,000 children (equally of both sexes) is large enough to effectively evaluate 5 many of the health outcomes identified in the Pease Feasibility Assessment literature review and the 6 recent systematic review (Rapazzo 2017) as potentially associated with PFAS in children. The health 7 outcomes and biomarkers studied would include mean difference in total cholesterol (ranging from 156 8 to 637 per stratum), uric acid levels (556 per stratum), estimated glomerular filtration rate (eGFR; 275 per 9 stratum), testosterone (about 400 per stratum) and insulin growth factor-1 (IGF-1; 146 per stratum). 10 Based on our estimations, we would also be able to detect differences in risk for obesity and atopic 11 dermatitis. A sample size of 2,000 children would be larger than many of the PFAS studies that evaluated 12 neurobehavioral outcomes such as IQ and ADHD (Wang 2015, Stein 2013, 2014, Fei 2011, Hoffman 2010, 13 Strom 2014).

An NHANES study of estimated glomerular filtration rate observed statistically significant findings with a total sample size of just under 2,000 children (Kataria 2015). For thyroid function, estradiol, delayed puberty, and asthma, a total sample sizes of 2,000 children may be sufficient, although larger sample sizes would be optimal (Lopez-Espinosa 2011, 2012; Stein 2016).

In summary, a total sample size of ≥2,000 would be sufficient to evaluate a wide range of biomarkers and
 outcomes including lipids (and hypercholesterolemia), uric acid (and hyperuricemia), estimated
 glomerular filtration rate, testosterone, IGF-1, neurobehavioral measures (executive function, attention,
 IQ) and ADHD, rhinitis, and obesity.

Health-related Endpoint	Relevant Study	Observed Effect Size	Assumptions	Sample Size/Stratum α error = .05 β error = .20
Total Cholesterol	Frisbee 2010, C8 Study	PFOS: 5 th vs 1 st quintile Age: <12 vrs 12-18	Mean PFOS serum levels were about 20	+4.6: 637/stratum
(mg/dL)	1,971 boys <12 yrs 2,773 boys 12-18 yrs 1,886 girls <12 yrs 2,520 girls 12-18 yrs	Boys: +6.2 +9.3 Girls: +4.6 +9.4	μg/L. SD for total cholesterol=29.3 mg/dL	+9.3: 156/stratum
High cholesterol		OR = 1.6	Prevalence=34.2%	300/stratum

22 **Table 1.** Sample size estimations for selected health-related endpoints in Child Study (ages 4-17 years)

Thyroid	Lopez-Espinosa 2012,	PFOS, 4 th vs 1 quartile:	Mean PFOS serum	1,080/stratum

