Assuming a 95% CI and 95% power, the sample size = 68/group.

a. TSH

In Ji 2012, the sample size was 633, \geq 12 years of age and the median TSH level was 1.37 µIU/mL with an IQR of 0.90, 2.01. The standard deviation was estimated as the IQR range divided by 1.35: (2.01 - .90)/1.35 = 0.82. This standard deviation was assumed for each group. For TSH, the linear regression coefficients for PFOS and PFHxS were 0.062 and 0.013, respectively. Using a PFOS level of 15 ng/mL and a PFHxS level of 9 ng/mL, the mean difference for PFOS and PFHxS are 0.93 and 0.12, respectively.

Assuming a 95% CI and 80% power, the sample size = 13/group for PFOS

Assuming a 95% CI and 80% power, the sample size = 733/group for PFHxS

b. TT₄ (total thyroxine)

In Ji 2012, the sample size was 633, \geq 12 years of age and the median TT₄ level was 7.4 µg/dL and the IQR was 6.7, 8.1. The standard deviation was estimated: (8.1 – 6.7)/1.35 = 1.04. This standard deviation was assumed for each group. For TT₄, the linear regression coefficients for PFOS and PFHxS were -0.021 and - 0.007, respectively. Using a PFOS level of 15 ng/mL and a PFHxS level of 9 ng/mL, the mean difference for PFOS and PFHxS are -0.32 and -0.06, respectively.

Assuming a 95% CI and 80% power, the sample size = 166/group for PFOS

Assuming a 95% CI and 80% power, the sample size = 4,716/group for PFHxS

Sample sizes for the categorical outcomes in Table 2 were based on the following prevalences in adults:

Hypercholesterolemia: 15% Hyperuricemia: 24% Thyroid disease: 6.5% (reported and confirmed by medical records); 11.5% (reported only) Elevated ALT: 11.2% Elevated GGT: 14% Elevated bilirubin: 1.1% Osteoporosis: 5% Osteoarthritis: 7.6% Cardiovascular disease: 13% Ulcerative colitis: 0.5% Rheumatoid arthritis: 1.2%

Health related Endpoints Not shown in Table 2:

Chronic kidney disease: 1.4% Liver disease: 2% Hypertension: 37% Pregnancy-induced hypertension: 8.5% Endometriosis: 7% Lupus: 0.2% Multiple sclerosis: 0.32% Kidney cancer: 0.3%

Multi-site Study – Eligibility Screening Script

Multi-site Study Eligibility Screening Script Flesch-Kincaid Readability Score – 5.8

> Form Approved OMB No. 0923-XXXX Exp. Date xx/xx/201x

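### The child uric acid size of 556 per stratum does not follow from the protocol's own difference and SD, which give 616; two adult sizes also miss their printed inputs, and the child eGFR SD differs between Table 1 and Attachment 3a

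*Protocol*

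**What the plan says.** Attachment 3 prints a sample size formula for a difference between two means and says of it: "This calculation is for a two-tailed hypothesis test and equivalent to using a 95% confidence interval to determine statistical significance". Attachment 3a fixes the error rates, with alpha "set at .05 and type 2 error" "set at .20. Sample sizes per stratum group were calculated".

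**Child uric acid.** Attachment 3a reports that "the mean uric acid level in the study population was 5.07 mg/dL with a SD of 1.19", and adds: "The sample size calculations assumed the same SD in the exposed children and the unexposed group". The Table 1 row gives SD 1.19, a difference of +0.19 mg/dL between the fourth and first PFOS quartiles, and 556 per stratum. Section 3.3.1 repeats the size in its argument that 2,000 children are enough: "uric acid levels (556 per stratum".

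**Adult elevated ALT by PFHxS.** Table 2 gives OR 1.37, a prevalence taken to be like that of the C8 study, and 1,570 per stratum. Attachment 3b lists, as a percentage, "Elevated ALT: 11.2".

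**Adult high cholesterol by PFHxS (Canadian survey).** Table 2 gives OR 1.57, prevalence 44%, and 290 per stratum.

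**Child eGFR.** Table 1 gives a difference of 6.6, SD 27.6 and 275 per stratum. Attachment 3a, which presents its notes as the parameters behind Table 1, gives a mean of 133 "with a SD of 23.9" and says that the calculations assumed the same SD in both groups.

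**The concern.** Sections 3.3.1 and 3.3.2 rely on these per-stratum sizes to argue which outcomes 2,000 children and 6,000 adults can evaluate. A reader should be able to recover each size from the effect, the SD or prevalence, and the error rates printed beside it. For child uric acid every input is printed, in two places that agree, and the size still does not come out. The printed figure is too small, so it claims more power than the inputs support. The ALT figure errs the other way, and the cholesterol figure is slightly too small. For eGFR the size agrees with Table 1 but not with the attachment meant to document Table 1.

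**Working it through.** **Means.** With equal SDs and equal strata, the Attachment 3 formula reduces to n = 2 × SD² × (1.96 + 0.8416)² / d², where (2.8016)² = 7.849.

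The formula reproduces other printed sizes:

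| Row | SD | d | Computed | Printed |
|---|---|---|---|---|
| Child total cholesterol | 29.3 | 4.6 | 636.9 | 637 |
| Child total cholesterol | 29.3 | 9.3 | 155.8 | 156 |
| Adult uric acid, C8 | 1.55 | 0.22 | 779.2 | 780 |
| Adult uric acid, NHANES | 2.5 | 0.44 | 506.8 | 507 |

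Child uric acid, with 2 × 1.19² × 7.849 = 22.23:

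- d = 0.19: 22.23 / 0.0361 = 615.8, so 616.
- d = 0.20: 22.23 / 0.0400 = 555.7, so 556, the printed figure.
- Rounding of the inputs does not explain it: d = 0.195 needs 585, and d = 0.195 with SD 1.185 still needs 580.
- Other variants at d = 0.19 also miss: one-sided 486, t-based 617, 90% power 825. Two-to-one allocation gives 924 and 462.

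Power at d = 0.19, as Φ(0.19 / SE − 1.96) with SE = 1.19 × √(2/n):

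| n per stratum | SE | Power |
|---|---|---|
| 556 (as printed) | 0.0714 | 75.9% |
| 500 (2,000 / 4) | 0.0753 | 71.4% |
| 667 (2,000 / 3) | 0.0652 | 83.0% |

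**Proportions.** Attachment 3 prints no formula for odds ratios, so the method has to be inferred from rows that reproduce. Take p0 as the unexposed rate, p1 = OR × p0 / (1 − p0 + OR × p0), p̄ = (p0 + p1) / 2, and n = 2 × p̄ × (1 − p̄) × 7.849 / (p1 − p0)².

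| Row | p0 | OR | p1 | Computed | Printed |
|---|---|---|---|---|---|
| Elevated ALT, PFOA | 0.112 | 1.54 | 0.1626 | 725.1 | 725 |
| Elevated ALT, PFOS | 0.112 | 1.25 | 0.1362 | 2,916.7 | 2,917 |
| Elevated ALT, PFHxS | 0.112 | 1.37 | 0.1473 | 1,418.9 | 1,570 |
| Same, with OR 1.35 | 0.112 | 1.35 | 0.1455 | 1,569.4 | – |
| High cholesterol, PFHxS | 0.44 | 1.57 | 0.5523 | 311.2 | 290 |

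With separate null and alternative variances, the last PFHxS ALT and cholesterol results at their printed odds ratios are 1,418 and 310. A continuity correction gives 1,474 and 328, neither of which is the printed value.

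**eGFR.** SD 27.6 and d = 6.6 give 274.5, so 275 as printed. SD 23.9 and d = 6.6 give 205.8, so 206.

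**The case against.** **The wrong input is not identified.** 556 also matches an SD of about 1.13 at 0.19 mg/dL, and Table 1 and Attachment 3a attach the SD of 1.19 to different NHANES adolescent papers. The slip could lie in the difference, the SD or the size. This stands, and it is why the fix starts with the sources. The SD of 1.19 is at least consistent between the two places.

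**The ALT prevalence is only assumed.** The PFHxS row says that the prevalence is similar to the C8 one. A rate of about 9.9% would give about 1,574, and reading 11.2% as the average of the two groups gives 1,610. But Attachment 3b lists 11.2%, the two sibling ALT rows reproduce with 11.2% as the unexposed rate, and neither reading of 11.2% gives 1,570.

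**Rounding of an odds ratio.** 290 is near the 286 to 287 that OR 1.6 would give. That may be its origin, but Table 2 prints 1.57.

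**The eGFR size is not wrong.** This stands. A reader might infer that 275 is a miscalculation, but it follows from its own row, and the row and the attachment cite different studies. Only the documentation conflicts.

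**Nothing turns on it.** For design this stands. 556 and 616 both exceed 500 per quartile and both fit within 667 per tertile, and the protocol accepts either split. The protocol also says that its estimates call for caution and that endpoints were not chosen on power.

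**Conclusion.** Three printed sizes do not follow from the inputs beside them:

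- Child uric acid: 616 rather than 556, 60 more per stratum (11%).
- Adult elevated ALT by PFHxS: about 1,420 rather than 1,570.
- Adult high cholesterol by PFHxS: about 310 rather than 290.

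The child eGFR SD is a separate contradiction between Table 1 and Attachment 3a. The uric acid result rests on the printed formula, two-sided 5%, 80% power and equal strata. The two adult results rest on the inferred two-proportion formula with the prevalence as the unexposed rate.

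A reader might go further and infer, from 1,570 × 4 = 6,280, that the protocol wrongly presents 6,000 adults as too few for liver function. The documents do not support that. Section 3.3.2 puts liver function at 3,000 to 4,000 in total and says that 6,000 may be sufficient. Tertiles of 2,000 would hold 1,570. The same table prints 2,917 for ALT by PFOS, so correcting 1,570 would not settle the question either way. Recruitment targets and the overall feasibility verdicts stay as they are. What changes is the accuracy of the stated sizes and of the power claimed for child uric acid. This point covers only the rows named and does not certify the rest of either table.

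**What to change.** Check the effect size, SD and prevalence of each of these rows against its cited source. If the printed inputs stand:

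- Replace 556 with 616 in Table 1 and section 3.3.1, and state about 71% power for 0.19 mg/dL at quartiles and about 83% at tertiles.
- In Table 2, replace 1,570 with about 1,420 and 290 with about 310.
- Make Attachment 3a and Table 1 name the same eGFR SD: 27.6 keeps 275, and 23.9 gives 206.

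If a source shows that a printed input is wrong, correct the input and recompute the row. The cost is a few table entries and one sentence in section 3.3.1. No participants are added and no analysis changes.
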